#### **Research Blood (for $\gamma$ -OHPdG level)**

At visits 1, 2, and 3, two green top tubes of blood will be drawn. The Research Blood at Visit 1 should be collected prior to agent administration. These samples will be used exclusively for developing non-invasive methods for testing biomarker detection.

#### **Research Urine (for $\gamma$ -OHPdG level and compliance)**

At Screen 2 and visits 2 and 3, one 100mL Urine sample will be collected. The Research Urine at Screen 2 will be used for  $\gamma$ -OHPdG levels and at visit 2 and 3 will be used for compliance to measure catechin levels.

#### **Research Blood and Urine PKs**

Six participants at Georgetown University will be given the option of participating in extra Research Blood and Urine PKs at Visit 1. The day before the pharmacokinetic study (Visit 1), Georgetown University study participants are instructed to fast after midnight except for drinking water. On the pharmacokinetic study day, study subjects skip breakfast and take no over the counter medications, vitamins, or health food products. Study participants come to the clinic in the early morning (6–8 a.m.) and are provided with food for breakfast. Immediately after or during breakfast, study subjects swallow their Polyphenon E capsules with a glass of water. Georgetown University study subjects are allowed unlimited water intake throughout the study day. Other drinks are not allowed. Two green top tubes of blood are collected before the administration of the Polyphenon E and then at time points 1.5, 3.5, and 8.5 hours (+/- 5 minutes) after drug administration. Study subjects self-collect urine before dosing and at each PK blood draw. After the 3.5 h blood collection, food for lunch is provided to the study subjects.

### **Study Agent**

Participants will receive Polyphenon E on Visit 1 (week 1 day 1) and Visit 2 (week 13 ± 3 days) for a twelve week supply of 840 pills. To give some flexibility to participants for Visit 2 (week 13), on Visit 1 (week 1 day 1), participants will be given one extra week drug supply of additional 70 pills, therefore on Visit 1 (week 1 day 1) participants will be given a supply of study agent of 910 pills, while on Visit 2 (week 13+/- 3 days), participant will be given a supply of study agent of 840 pills.

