#### **2.4.2 Supply of Polyphenon E for this study**

The Chemopreventive Agent Development Research Group, Division of Cancer Prevention, National Cancer Institute, NIH is supporting this clinical study by providing Polyphenon E as 200 mg capsules. The capsules will provide 200 mg of EGCG each. Participants will take 2 - 5 capsules once or twice per day continuously for six months, according to the dose escalation 3 + 3 design. Polyphenon E/EGCG capsules will be stored at room temperature, avoiding direct sun exposure.

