## **5.2 Polyphenon E Administration**

The study agent will be self-administered by the subject. Participants will be instructed to take each dose of Polyphenon E after a light meal.

The medication will be released by the research pharmacies at GUH or UPR every 12 weeks; thus on Visit 1 (week 1, day 1), and Visit 2 (week 13 +/- 3 days). A participant diary will be provided. In order to give participants some flexibility for Visit 2 (week 13 +/- 3 days), patient will be provided one extra week of medication, so they will not run out of medication before they receive the medication on Visit 2 (week 13 +/- 3 days). Participants will have their diary reviewed and a pill count performed at their Visit 2 (week 13 +/- 3 days) and Visit 3 (end of intervention, week 25 +/- 3 days).

Polyphenon E/EGCG will be administered orally at a doses of 400 mg qd, 400 mg bid, 600 mg bid, 800 mg bid, 1000 mg bid on a continuous dosing schedule for a total of 24 weeks, according to the dose escalation 3 + 3 design. Participants are instructed to take their medication after a light meal. The meal should not include either milk or juice during the meal. If a dose is missed, the participant should not make up the missing dose the next day, as this would result in an extra dose for that day. Participants should not make up vomited doses. The missing dose or vomited dose should be recorded in the medication diary.

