## **5.7 Adherence/Compliance**

5.7.1 All toxicity and samples from all subjects who receive drug will be evaluated and included in the primary analysis, which will be based on intent to treat principle.

5.7.2 The unused pill count and/or participant diary will be provided to and collected from participants by the study coordinator every 3 months during clinic visits for the 6 months of Polyphenon E treatment.

5.7.3 Additionally, an adequate record of receipt, distribution, and return of all study drugs must be kept in a pill count form for the pharmacist to complete.

5.7.4 Measuring the three major metabolites (EGCG, EGC, and EC) of green tea catechins in urine will provide additional evidence of compliance. Pill count and diary are usually used for compliance, however these parameters could be misreported or tampered by participants. For this purpose, urine samples will be collected at Visit 2 and Visit 3.

Subject compliance with the treatment and protocol includes willingness to comply with all aspects of the protocol, and to have blood collected for all safety evaluations. At the discretion of the principal investigator, a subject may be discontinued from the trial for non-compliance with follow-up visits or study drug.

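### Section 7.6 states one capsule supply for every participant, which fits only 1000 mg bid; at the four levels used it is 1.25 to 5 times the amount implied by the assigned dose

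*Combined protocol and SAP*

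**What the plan says.** Section 7.6, under Study Agent, gives the supply in numbers. Drug is dispensed at Visit 1 and Visit 2 "for a twelve week supply of 840 pills". At Visit 1, "participants will be given one extra week drug supply of additional 70 pills", so that "participants will be given a supply of study agent of 910 pills" at that visit; the Visit 2 supply is again 840. The paragraph speaks of participants in general and names no dose level.

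The dose sections describe an escalation. On capsule strength, Section 2.4.2 says: "The capsules will provide 200 mg of EGCG each". On the number to be taken, it says: "Participants will take 2 - 5 capsules once or twice per day continuously for six months, according to the dose escalation 3 + 3 design". Table 3 in Section 5.1 lists five levels, and Section 5.2 repeats them: "at a doses of 400 mg qd, 400 mg bid, 600 mg bid, 800 mg bid, 1000 mg bid". Section 5.6 plans no dose modification once a participant has started.

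Other passages give the supply only as a length of time. Section 5.2 has the pharmacies release drug every 12 weeks, with one spare week before Visit 2. Footnote o to the Schedule of Events (Section 7.1) has a three-month supply at each of the two visits.

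On adherence, Section 5.7 says: "The unused pill count and/or participant diary will be provided to and collected from participants". Sections 5.1, 5.2 and 7.1 place the pill counts at Visits 2 and 3. No formula for adherence is given. Section 6.5 requires the quantities dispensed to and returned by each participant to be recorded.

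Table 6 in Section 13.1 shows 3, 3, 3 and 4 participants starting treatment in Cohorts 1 to 4 (400 mg QD, 400 mg BID, 600 mg BID and 800 mg BID). No one was enrolled at 1000 mg bid.

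**The concern.** In a dose-escalation study the number of capsules a participant needs depends on the assigned level. Section 7.6 is the only place that states a quantity to dispense, and it states the same one for everybody. It is current operative text. It is also consistent in itself (840 + 70 = 910), so it does not look like a slip in one digit.

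Two things are at stake. First, a pharmacy following the paragraph as written would release more capsules than the assigned dose calls for at every level that was used. The agent is one for which the protocol requires weekly or bi-weekly liver tests, a hepatotoxicity algorithm (Appendix D) and study-hold rules (Section 8.5). Second, pill count is a stated compliance measure without a stated denominator, and 840 and 910 are the only quantities in print that someone deriving adherence could pick up.

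**Working it through.** **Inputs**

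- Capsule strength: 200 mg EGCG (Section 2.4.2).
- Dose levels: 400 mg qd, then 400, 600, 800 and 1000 mg bid (Table 3; Section 5.2).
- Dispensing periods: 12 weeks = 84 days; with the extra week at Visit 1, 13 weeks = 91 days (Section 5.2).
- Stated supply: 840 for 12 weeks, 70 for the extra week, 910 at Visit 1 and 840 at Visit 2 (Section 7.6), a total of 1,750.
- Participants who started treatment: Table 6, Section 13.1.

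**Formula**

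Capsules per day = daily EGCG dose / 200 mg. Implied supply = capsules per day × days.

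**Reproducing the plan's figures**

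At 1000 mg bid: 2000 / 200 = 10 capsules a day. Then 10 × 84 = 840, 10 × 7 = 70 and 10 × 91 = 910. All the stated figures are reproduced exactly, at this level only.

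**All five levels**

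| Level | Started | Capsules/day | Implied, 84 days | Implied, 91 days | Implied total | 840 / implied 84-day supply | Stated total minus implied total |
|---|---|---|---|---|---|---|---|
| 400 mg qd | 3 | 2 | 168 | 182 | 350 | 5.0 | 1,400 |
| 400 mg bid | 3 | 4 | 336 | 364 | 700 | 2.5 | 1,050 |
| 600 mg bid | 3 | 6 | 504 | 546 | 1,050 | 1.67 | 700 |
| 800 mg bid | 4 | 8 | 672 | 728 | 1,400 | 1.25 | 350 |
| 1000 mg bid | 0 | 10 | 840 | 910 | 1,750 | 1.0 | 0 |

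The ratio is the same at Visit 1: 910 / 182 = 5.0, 910 / 364 = 2.5, 910 / 546 = 1.67 and 910 / 728 = 1.25. The implied counts are simply what the protocol's own doses and capsule strength give. They are shown to measure the disagreement and are not put forward as a dispensing rule.

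**Does another passage resolve it?**

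Section 5.2 and footnote o of Section 7.1 describe supply by time. That is compatible with a quantity that follows the dose, but neither says that the figures in Section 7.6 apply to one level or are to be scaled. Because Section 5.6 plans no dose change after the start, the larger figure cannot be an allowance for escalation within a participant.

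**Pill count, conditional on a wrong denominator**

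If 840 were used as the expected count for a 12-week period, a participant who took every capsule would show 168/840 = 20%, 336/840 = 40%, 504/840 = 60% or 672/840 = 80% in Cohorts 1 to 4. If adherence is taken as dispensed minus returned over capsules due, the same participant shows 100% at every level, however many capsules were handed out.

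**The case against.** The arithmetic is hard to dispute; the objections concern what follows from it.

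The other supply passages are written in weeks or months, and Section 5.1 ties administration to the level assigned to each cohort. Read with these, Section 7.6 may be one unscaled paragraph that quotes the figure for the highest level, and the pharmacies may have scaled it as a matter of course. This is plausible, but the documents do not say it.

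A reader might infer that participants were in fact given up to five times their supply. The documents do not support that, because nowhere do they report what was dispensed. A reader might also infer that the pill count is taken against the wrong base. That is not supported either: no passage uses 840 or 910 as a denominator, and the records required by Section 6.5 allow capsules taken to be derived from actual quantities. Dividing an 84-day need by 910 would also overstate the problem, since it mixes the planned spare week with the dose mismatch. Even at 1000 mg bid, where 910 fits, it gives 840/910 = 92.3%.

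No planned analysis is shown to depend on the count. Section 13.8 bases the primary analysis on all subjects who receive drug, and Section 13 defines no adherence-based analysis set or exclusion. Section 5.7 acknowledges that pill counts and diaries can be misreported and adds urine catechins at Visits 2 and 3.

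Finally, enrollment has stopped, so a change to Section 7.6 is unlikely to alter dispensing.

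These arguments limit the consequences. They leave standing a stated operative quantity that disagrees with every dose level used.

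**Conclusion.** The point holds as an internal contradiction. The single supply in Section 7.6 matches only 1000 mg bid, a level at which no one was enrolled. At the four levels used it is 5.0, 2.5, 1.67 and 1.25 times the amount implied by the assigned dose. Followed literally over both visits, that is 1,750 capsules against 350, 700, 1,050 or 1,400. This rests on 200 mg capsules, the levels in Table 3, and dispensing periods of 13 and 12 weeks, all of which the protocol states.

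The finding goes no further than the text. Over-dispensing is a possibility to be checked in the records, and a distorted pill count is a risk only if 840 or 910 serves as the expected count. No effect on the primary analysis is shown. The correction is still worthwhile, because the paragraph concerns the quantity released of an agent under hepatotoxicity monitoring, and because adherence in the 13 treated participants can still be derived correctly.

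**What to change.** 1. Reconcile Section 7.6 (Study Agent) with Section 2.4.2, Table 3 in Section 5.1, Section 5.2 and footnote o of Section 7.1, so that the stated quantity agrees with the assigned dose level. How the supply is to be set is for the sponsor and investigators to decide.
2. Check the accountability records required by Section 6.5 for the 13 treated participants, and note what was dispensed and returned at each visit.
3. State how pill-count adherence is derived: recorded dispensed minus returned, divided by capsules due at the assigned level, and not against 840 or 910. Allow in the denominator for holds and discontinuations directed by Section 5.6 and Appendix D, so that a participant who stopped as instructed is not counted as non-adherent.

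The cost is a short correction to Section 7.6, one or two lines in the adherence derivation, and a review of dispensing records for 13 people. No new data need be collected. With enrollment closed, items 2 and 3 carry most of the remaining value.

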### **Adverse Event (AE) Monitoring**

The investigator or qualified designee will assess each subject to evaluate potential new or worsening AEs as specified in 7.1 SCHEDULE OF EVENTS, and more frequently if clinically indicated. Adverse experiences will be graded and recorded throughout the study and during the follow-up period according to NCI CTCAE Version 4.0 (see Section 11.2). Toxicities will be characterized in terms regarding seriousness, causality, toxicity grading, and action taken with regard to trial treatment.

### **Full Physical Exam**

The investigator or qualified designee will perform a complete physical exam and vital signs assessment during the screening period. Clinically significant abnormal findings should be recorded as medical history.

### **Vital Signs**

The investigator or qualified designee will take vital signs at screening, prior to the administration of each dose of trial treatment and at treatment discontinuation as specified in the protocol section 7.1 Schedule of Events. Vital signs should include temperature, pulse, respiratory rate, weight and blood pressure. Height will be measured at screening only.

### **Liver and Abdominal MRI/CT scans, and Other Imaging**

A comprehensive liver and abdominal ultrasound, MRI or CT scan will be performed at the Screen 1 or Screen 2 Visit if not performed within 3 months prior to consent, and at the end of intervention (± 3 weeks from Visit 3) as specified in section 7.1 Schedule of Events. Image evidence of cirrhosis and HCC will be recorded and followed. These are standard-of-care tests which are usually performed at 6-month intervals in participants with cirrhosis.

### **Standard Laboratory Tests**

Standard laboratory samples for this study will be assessed using the certified laboratories at the investigators' institutions, or at a clinical laboratory such as Quest or LabCorp. The PI or sub-investigator will review, initial, and date all laboratory results. Any laboratory value outside the reference range that is considered clinically significant by the investigator will be followed as appropriate. Clinically significant laboratory values will be recorded as adverse events if they meet the criteria as specified in Adverse Events (NCI-CTCAE) version 4.0).

## **8. CRITERIA FOR EVALUATION AND ENDPOINT DEFINITION**

### **8.1 Primary Endpoint**

8.1.1 To establish maximum tolerated dose (MTD) and to collect safety data of Polyphenon E/EGCG treatment in participants with cirrhosis

The safety data of Polyphenon E treatment in participants with liver cirrhosis will be collected at the monthly visit for the first 3 cycles, then at the end of treatment visit for 4th to 6th cycle of treatment). Safety data on hepatotoxicity will be obtained by weekly or bi-weekly (depending on assigned dose, clinical stability, and liver biochemical stability of the participant) liver function tests. Participants who experience hepatotoxicity according to Appendix D will be re-evaluated every 3-4 days until resolution.

Safety and adverse event data will be summarized using descriptive (frequency, %) statistics by dose cohort. The primary endpoint of MTD cannot be established because the study was closed early, and, based on the observed safety profile with a single DTC occurring in dose cohort 4 (1/4 patients), future studies can consider dose level 3 as the starting dose.

8.1.2 To determine the effects of Polyphenon E/EGCG treatment on the suppression of  $\gamma$ -hydroxy-1,N(2)-propanodeoxyguanosine ( $\gamma$ -OHPdG) levels in cirrhotic liver.

Our preliminary data shows that  $\gamma$ -OHPdG predicts HCC development. Among the 3 anti-oxidants—Theaphenon E, lipoic acid, and vitamin E—used in 3 HCC animal models, only Theaphenon E effectively suppressed the accumulation of  $\gamma$ -OHPdG and prevented HCC development. Theaphenon E contains the same active components—epigallocatechin gallate (EGCG), epigallocatechin (EGC), and epicatechin (EC)—as the dietary antioxidant, Polyphenon E. EGCG has been tested in many clinical cancer prevention trials. We propose that the accumulation of the DNA adduct,  $\gamma$ -OHPdG, predicts the development of HCC, and that Polyphenon E suppresses the formation of  $\gamma$ -OHPdG, which may reduce HCC development in participants with cirrhosis. In this pilot study, our primary endpoint is to determine the effect of EGCG treatment on  $\gamma$ -OHPdG levels in cirrhotic liver. During screening, subjects will have a baseline biopsy taken. Only subjects found to have high  $\gamma$ -OHPdG levels (IHC score equal or higher than 3) in their cirrhotic liver will receive EGCG treatment for 24 weeks. An exit liver biopsy will be taken at the end of intervention and will be compared with the baseline biopsy for changes in liver  $\gamma$ -OHPdG levels. All liver tissue slides from the biopsy will be processed and stained with an anti-  $\gamma$ -OHPdG antibody in the lab of [name]. Two pathologists: [name] from GU and [name] [name] from UPR will review the slides and score the level of  $\gamma$ -OHPdG in the participant liver biopsy samples.

